C.4.b. Visit 2 (Baseline Visit): 7-14 days after the screening visit, eligible subjects will return for a baseline visit where subjects will be trained to record their mood, desire to drink, self-efficacy and daily drinking using the IVR system and a physical examination will be performed by a study physician or APRN and any medication questions reviewed. Subjects will be instructed in use of study medication and given their initial 4 mg dutasteride or placebo dose and instructed to take two capsules (1 mg) daily at home for the remainder of the 12-week treatment period. Subjects will receive study medication for home use at the baseline and at each follow-up visit. At the baseline visit subjects will receive a one-week back-up supply of medication for use in case of lost capsule or need to reschedule bi-weekly follow-up visits. Subjects will be asked to bring unused medication to each follow-up visit for monitoring medication use. The UCHC research pharmacy will randomly assign subjects to dutasteride or placebo using an urn randomization to balance subjects on AKR1C3 genotype, age and baseline alcohol use. Medication will be delivered or picked up from UConn Health IDS pharmacy for distribution to patients during IDS office hours (M-F 7:30am-4pm). For IDS off-hour appointments, medication may be obtained from IDS pharmacy and kept with study staff in a locked cabinet in a locked office in preparation for that appointment. In case a patient has a last minute cancellation or is a no-show, medication can be kept with study staff until the end of the business week. If the product is not distributed to the patient during that time, it will be returned to pharmacy.

C.4.c. Bi-weekly Clinic Visits 3 - 8: A brief Timeline Follow-Back Interview will be performed to track participants' daily alcohol consumption to augment IVR reports of alcohol use (see section D.9.a.2) and a trained research staff member will deliver the medical management intervention. Blood samples for study outcome measures (GGT, %dCDT, 3α -diolG, and testosterone) will be obtained at visits 5 and 8 (mid-point and end of treatment). We chose biweekly medication monitoring visits during the treatment period in order to optimize tolerability and thereby enhance treatment retention.

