c. *Psychiatric diagnosis:* The Structured Clinical Interview for DSM-IV (SCID-I/P) (First et al. 1997) will be used to classify subjects according to the presence or absence of major psychiatric disorders including AD. This, together with the physician's unstructured psychiatric interview (visit 2), will be used to assess exclusion criteria for serious psychiatric disorders. The SCID-I/P will be administered at screening visit and the alcohol portion of the SCID will be administered at treatment end-point and the 2, 4, and 6-month follow-up visits to evaluate presence of current alcohol dependence criteria after treatment.

d. *Family history of alcohol dependence:* This interview systematically questions an informant about the presence of psychiatric illness in relatives. We will use the alcohol section of the Family History Assessment Module FHAM (Rice et al. 1995) the subject will be asked to provide information concerning his biological relatives history of alcohol use, however, names of family members will not be obtained.

Table 1: Schedule of Assessments

Study Visit	V 1 Screening	V 2 Baseline	Bi-weekly phone call	V 3-7	V 8 End-point	V 9: 2-mo follow-up	V 10: 4-mo follow-up	V 11: 6- mo follow-up
Time relative to Medication		Start medication	wks 1,3,5	wks 2, 4,6,8,10	Wk 12 End medication			
Medical History, SCID, Fam Hx, Clinical lab tests, blood for DNA	X							
Timeline Follow-Back Interview	X	X		X	X	X	X	X
Vital signs & weight	X	X		X	X			
Alcohol Effects Questionnaire	X				X		X	X
Study outcome blood samples	X			wk 6	X	X	X	X
Physical Exam & Clinician review of Medical History		X						
Penn Alcohol Craving Scale (PACS)		X		X	X	X	X	X
SIP, DMQ, BDI, STAI		X		wk 6	X	X	X	X

Daily IVR call		X	X	X	X			
Side Effect Checklist			X	X	X	X		
Medical Management		X		X				
MED-Q					X			
Follow-up Interview (Alcohol SCID)					X	X	X	X

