d. *Daily Events:* Participants will be asked whether they experienced a list of nine possible daily events (3 stressful, 3 pleasant, and 3 situations where someone might drink). These measures will be used to assess the influence of positive and negative events on drinking.

e. *Daily medication usage:* Using IVR, subjects will report daily medication use. Additionally, at each bi-weekly study visit, subjects will be asked by the study staff to indicate the number of study drug capsules taken each day. This method has been shown to be highly correlated with electronic monitoring of medication adherence (Feinn et al. 2003).

C.6.b.3. Areas assessed biweekly during the active treatment period and follow up visits:

a. *Alcohol use patterns:* The TLFB (Sobell and Sobell 1992) will be used to estimate drinking at intake, at each biweekly study visit during the active treatment period and at each of the two follow-up evaluations. This interview procedure will provide quantity/frequency of alcohol consumption data for each day during the period prior to the interview. We will also be collecting daily measures of alcohol consumption using IVR during the active treatment period because despite evidence of the reliability and validity of the TLFB when used by trained interviewers, the TLFB is less useful for detecting patterns of alcohol consumption that vary on a day-to-day basis (Carney et al. 1998; Searles et al. 2000). Daily IVR reports will also enable us to examine co-variation in daily mood and daily events with alcohol use in order to address whether dutasteride moderates associations between daily mood or daily events and drinking as our group has found using IVR methods for treatment with naltrexone (Kranzler et al. 2004; Armeli et al. 2006).

b. *Alcohol Craving:* The Penn Alcohol Craving Scale (PACS) is a 5-item self-report measure that includes questions regarding the frequency, intensity, and duration of craving over the past week as well (Flannery et al., 1999). The PACS has been shown to predict subsequent drinking during alcohol treatment trials (Flannery et al., 1999, 2003).

c. *Medication adverse effects:* Subjects will provide reports of side effects at each bi-weekly phone visit and study visit during the active treatment phase and 2-month follow-up visit using a list of adverse medication

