Efficacy analyses will be performed using linear mixed models implemented in SPSS. Medication group will be treated as a factor and treatment week as a continuous covariate. An interaction term between medication group and week will be used to evaluate the efficacy of dutasteride compared to placebo in reducing drinking behavior over time. Pretreatment drinking will be controlled for using TLFB drinking data for the month prior to screening as a covariate. Treatment goal (stop vs. reduce drinking) will also be included as baseline covariate. The robustness of results will be evaluated by running the model under three different conditions: 1) all provided information, 2) only completers, and 3) imputation where missing days are coded as HDDs for subjects who fail to complete treatment.

For aim 3, analysis of drinking outcome variables will be repeated by including genotype at the *AKR1C3* rs12529 polymorphism as an additional between-subject factor.

C.8.a.3 Examination of daily measures.

Multilevel models will be used to examine the relations among daily measures of mood, daily event triggers and the frequency of drinking and of heavy drinking (level 1 measures) and their moderation by medication (level 2 measure). To examine how the within-person processes vary across individuals (i.e., cross-level medication interactions), the level 1 parameters are considered as outcomes in the level 2 model. Of specific interest is how the level 1 slopes (e.g., the associations between mood or daily event triggers and heavy drinking) vary as a function of experimental condition (dutasteride vs. placebo). Control variables (baseline heavy drinking, depression symptom score, baseline AD symptom severity) will also be included in level 2 predictive models. The utility of each level 2 predictor will be determined by the significance tests of the level 2 partial regression slopes.

C.8.b. Sample size considerations:

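### The Visit 2 craving score (PACS), which the protocol calls predictive of later drinking, is unused in the efficacy model: a small possible gain in precision, no bias

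*Combined protocol and SAP*

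**What the plan says.** Section C.6.b.3.b introduces the Penn Alcohol Craving Scale as a short self-report with "questions regarding the frequency, intensity, and duration of craving over the past week", and gives one reason for its use: "The PACS has been shown to predict subsequent drinking during alcohol treatment trials". Table 1 schedules it at Visit 2, Visits 3 to 7, Visit 8 and the three follow-up visits, which makes 1 + 5 + 1 + 3 = 10 occasions.

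Section C.8.a.2 sets out the efficacy model. The test is described thus: "An interaction term between medication group and week will be used to evaluate the efficacy of dutasteride compared to placebo". Two covariates are named: "Pretreatment drinking will be controlled for using TLFB drinking data for the month prior to screening as a covariate" and "Treatment goal (stop vs. reduce drinking) will also be included as baseline covariate".

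PACS appears nowhere in C.8. It is not a primary or secondary outcome and not an efficacy covariate. It is not among the Aim 4 person-level controls either: "Control variables (baseline heavy drinking, depression symptom score, baseline AD symptom severity) will also be included in level 2 predictive models". Nor is it among the urn randomization variables in C.3.c.

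Visit 2 is also the first dosing visit, at which men are "given their initial 4 mg dutasteride or placebo dose" (C.4.b), and it holds the first medical management session (C.5.a). The order of PACS relative to either is not stated.

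**The concern.** A baseline measure that predicts the outcome is what one wants in the adjustment set of a randomized comparison. It removes outcome variance unrelated to treatment and corrects for chance imbalance in that measure. PACS is described in those terms, is already collected at baseline, and is then left out.

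Precision is not plentiful here. C.8.b powers the trial for d=0.45, while the same section reports d=0.37 from the naturalistic study and d=0.3 from the pilot. Section C.8.a.2 also says that baseline group differences will be looked for, without saying what follows if one is found. If craving turned out imbalanced, adjusting for it would be a choice made after seeing the data. Naming the covariate now removes that choice.

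**Working it through.** **Inputs from the documents.** 80 men per arm, α=0.05, d=0.45, stated power 80%, earlier effects of d=0.37 and d=0.3 (C.8.b); 12 treatment weeks; 176 randomized for 160 completers, so 16/176 = 9.1% loss.

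**Inputs assumed.** A two-sided test. A partial correlation r of 0.1 to 0.4 between Visit 2 PACS and on-treatment drinking, given the two planned covariates. For the slope test, a random intercept and slope (C.8.a.2 does not state the random effects) with illustrative variances. The documents give no correlation of any kind for PACS.

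**Step 1: the plan's own figure.** A two-sided, two-sample t-test with 80 per arm and d=0.45 has power 80.8%. The stated 80% therefore reproduces as a comparison of means.

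**Step 2: mean-level contrast.** Adjustment multiplies the residual variance by 1 − r², so the effective effect size is d/√(1 − r²). The equivalent unadjusted total sample is 160/(1 − r²).

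| r | Effective d (from 0.45) | Power, d=0.45 | Power, d=0.37 | Power, d=0.30 | Equivalent n |
|---|---|---|---|---|---|
| 0 | 0.450 | 80.8% | 64.3% | 47.1% | 160 |
| 0.1 | 0.452 | 81.1% | 64.7% | 47.4% | 162 |
| 0.2 | 0.459 | 82.3% | 66.1% | 48.6% | 167 |
| 0.3 | 0.472 | 84.3% | 68.4% | 50.7% | 176 |
| 0.4 | 0.491 | 87.0% | 71.8% | 53.9% | 190 |

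**Step 3: planned medication-by-week test, PACS as a main effect only.** A time-constant covariate explains differences in level between men, not differences in slope. Generalized least-squares standard errors were computed for 12 weeks, 80 per arm and about 9% early dropout, with intercept variance 1, slope SD 0.05 and residual variance 0.64. With PACS explaining about 2% to 20% of the intercept variance, the standard error of medication-by-week is 0.9999 to 1.0000 of its unadjusted value. The standard error of the average group difference falls to 0.91 to 0.99 of its value.

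**Step 4: planned test, PACS plus PACS-by-week.** Let ρ be the correlation of PACS with a man's true slope, and f the share of the variance of estimated slopes that is true between-man variance. With complete data the standard-error ratio is √(1 − ρ²f).

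- ρ=0.1, f=0.2: √(1 − 0.002) = 0.999, a fall of 0.1%.
- ρ=0.4, f=0.5: √(1 − 0.08) = 0.959, a fall of 4.1%.
- ρ=0.4, f=0.85: √(1 − 0.136) = 0.930, a fall of 7.0%.

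Under the Step 3 variances, f = 0.05²/(0.05² + 0.64/143) = 0.36, where 143 is the sum of squared centred weeks. The fall is then 0.2% at ρ=0.1 and 2.9% at ρ=0.4.

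**Step 5: price if the covariate is useless.** In 40 simulated trials in which PACS had no relation to slope, adding both terms raised the medication-by-week standard error by about 0.4% to 0.6%. At the bottom of the Step 4 range the net gain can therefore be nil.

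**The case against.** The strongest objection is that the gain in power belongs to a different test. A reader might infer from Step 2 that the planned analysis gains up to six points of power, or the equivalent of 2 to 30 extra men. The documents do not support that: efficacy is judged by medication-by-week, and for that test only the PACS-by-week term can help. This part stands in full.

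Second, the protocol says that PACS predicts drinking. It does not say that the baseline score, as opposed to scores during treatment, adds to pretreatment drinking and treatment goal, and it says nothing about slopes. This also stands, and it is why r and ρ are shown as assumed ranges. A related point is that C.8.b does not say whether d=0.45 is standardised on a raw or a residual SD. If it is the raw SD and the planned covariates correlate 0.5 with the outcome (assumed), mean-level power is already 90.4%, and PACS takes it only to 90.7% to 94.6%.

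Third, a reader might infer that the omission biases the treatment effect, or that including PACS would close the gap between d=0.45 and the earlier effects. Neither follows. Leaving out one optional covariate does not bias a randomized comparison, and the urn already balances several drinking measures. At d=0.30, even the favourable mean-level calculation reaches only 53.9%.

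Fourth, other baseline scales could be proposed on similar grounds, and C.6.b says that the assessments were chosen partly to cover several outcome domains. That is fair. PACS differs in that its only stated rationale is prognostic, whereas the depression, anxiety, motives and expectancy scales each have a stated exploratory or monitoring use.

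**Conclusion.** The point holds as a minor, low-cost improvement. That PACS is collected at baseline, is described as predictive and is absent from the efficacy model can be confirmed directly from the text. The size is uncertain and may be small: for the planned medication-by-week test, essentially nothing from a main effect, and roughly 0.1% to 7% off the standard error from PACS-by-week, before the small cost in Step 5. The mean-level power gain of 0.3 to 6.2 points at d=0.45 applies only if a contrast of average drinking is reported. All of this rests on assumed correlations of 0.1 to 0.4 and illustrative variances. The validity of the planned comparison is not in question.

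**What to change.** In C.8.a.2, pre-specify the Visit 2 PACS total and its interaction with week as baseline covariates in the SDs/week and HDDs/week models. For a missing baseline score, use the sample mean with a missing indicator. In C.4.b, state that PACS is completed before the first study dose and before the first counselling session, so that the score is a clean baseline.

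The cost is one or two sentences in the analysis section and one on the order of Visit 2. The model gains two parameters, or three if the missing indicator is needed, among 176 randomized men, and no new data are collected. The drawback is that the gain may be small or nil if PACS adds little to the covariates already planned.

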Subjects: 39 subjects were randomized to study medication or placebo, 36 have completed 8 weeks of medication. Participants enrolled in the study averaged 52.7 ± 8.9 (s.d.) years of age, 82% of whom met criteria for AD and consumed on average of 46 ± 20 (s.d.) SDs / week with 5.1 ± 1.9 (s.d.) HDD / week at study entry. 50% of subjects had a family history of alcohol dependence and 73% identified a goal of reducing drinking while 27% identified a goal to stop drinking.

Safety: Study medication has been well tolerated with similar rates of side effect reports for dutasteride vs. placebo during the 8-week medication treatment phase [mean number of side effects reported / subject: dutasteride= 6.0 ± 5.8 (s.d.) vs. placebo= 8.4 ± 10.8 (s.d.)]. The number of subjects reporting a sexual related side effect was also been similar between the two arms ($n=3$ for dutasteride and $n=4$ for placebo). Three subjects dropped out of treatment during the 8-week active phase (2 placebo, 1 active drug) and none due to medication side effects. Participation in completing daily self-reports was high [$90\% \pm 10$ (s.d.) of possible reports].

Laboratory measure of drug effect for the first 15 subjects showed a significant reduction in serum 3 α -diolG for subjects randomized to dutasteride ($n=9$) at both 4-weeks (84% reduction; $p=0.003$) and 8-weeks (86% reduction; $p=0.002$) demonstrating effective inhibition of 5AR activity with the dutasteride dosing schedule proposed. There was no effect of dutasteride on serum testosterone levels at either 4- or 8-weeks ($p=0.42$ and 0.15 respectively) in this sample of heavy drinkers which mirrors the lack of effect of dutasteride on serum testosterone in other samples (Clark et al. 2004). There was no significant change in serum 3 α -diolG or testosterone in subjects in the placebo group ($n=6$).

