C.3.a. Dutasteride will be purchased commercially and formulated in opaque capsules by the Research Pharmacy Service of John Dempsey Hospital. Placebo will be formulated to match the active medication. Subjects will receive 4 mg of dutasteride or matching placebo capsules during first treatment visit (baseline study visit 2) followed by 1 mg daily for 12 weeks.

C.3.a.1. Pharmacodynamics: Dutasteride, a synthetic 4-azasteroid compound, is a competitive and specific inhibitor of both type I and type II steroid 5 α -reductase with which it forms a stable enzyme complex with extremely slow dissociation. At clinical doses, larger reductions in DHT concentrations were observed with dutasteride than with finasteride, due to the limited inhibition of human type I 5AR by finasteride (Gisleskog et al. 1998; Gisleskog et al. 1999). In humans, type I 5AR is present in the brain, liver, adrenal gland and skin and is responsible for approximately one-third of circulating DHT. Type II 5AR is also present in the liver, is the predominant form in the prostate, and is responsible for two-thirds of circulating DHT. For studies of alcohol use, inhibition of type I 5AR may be of particular importance, as type I 5AR but not type II enzyme is present in the adult brain (Lephart et al. 2001) where local generation of neuroactive steroids is thought to occur in addition to peripherally generated neuroactive steroids in the liver and adrenal gland.

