effects derived from prior studies of dutasteride (any ongoing potential medication side effects reported at the 2-month follow-up will be assessed again at 4- and 6-month follow-up visits as needed).

d. Measures of treatment received: Records of all medication taken will be recorded. The study staff will also record the number of contact hours subjects have been exposed to for any treatment outside of the study that is related to their drinking to identify if this variable might need to be considered as a covariate in outcomes analysis.

C.6.b.4. Areas assessed at intake, midpoint, end of treatment and at follow-up visits:

a. Alcohol-related problems: The Short Inventory of Problems (SIP). The SIP is a 15-item instrument derived from the Drinker Inventory of Consequences (DrInC), which was developed for use in Project MATCH as a measure of alcohol-related consequences.

b. Psychological symptoms: a) The Beck Depression Inventory (BDI), a 21-item self-report measure of depressive symptoms, yields a total score that ranges from 0 to 63 (Beck et al. 1961). The BDI is generally regarded as a sensitive self-report measure of depressive symptoms, and will be used to explore the relation between depressive symptoms and treatment. b) The State version of the Spielberger State-Trait Anxiety Inventory (STA), a 20-item self-report questionnaire (Spielberger 1983), will be used to provide concomitant monitoring of anxiety symptoms.

c. Drinking Motives: Drinking motives will be measured with the Drinking Motives Questionnaire [DMQ; (Cooper et al. 1992; Cooper 1994)] to explore potential changes as a result of treatment in drinking motives. This instrument contains 20 items with 4 subscales, drink to a) cope motives (e.g., "Because it helps when you are feeling nervous or depressed"), b) conformity motives (e.g., "Because it helps me fit in"), c) enhancement motives (e.g., "Because it's fun"), and d) social motives (e.g., "Because it makes a social occasion more enjoyable"). The DMQ will be administered at baseline and for those subjects who continue to drink again at midpoint, end of treatment and at the 2,4, and 6-month follow-up visits.

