C.8.a.1. Safety: Safety will be analyzed using categorical outcomes, defined by the type and severity of adverse effects. Summary measures of adverse events (AEs) will be developed by organ system from the adverse event checklist and will be compared for patients receiving dutasteride or placebo using χ^2 analysis. Comparisons will be conducted on 1) the number of patients in each of the two groups who report AEs, 2) the number of patients in each of the two groups who report moderate-to-severe AEs, and 3) the number of patients in each group who discontinue treatment due to AEs. Individual AEs that occur in $\geq 5\%$ of patients in either medication condition will be examined using χ^2 analysis.

C.8.a.2. Efficacy: An important initial consideration will be to identify baseline differences between groups that may have occurred despite the use of urn randomization. The distribution of outcome data will also be examined prior to analysis, to determine the need for transformation and whether parametric analytic methods can be utilized. Successful outcome will be defined in terms of three primary dependent measures: SDs/week, HDDs/week, % of subjects with no HDDs, and % of subjects with non-hazardous drinking (no HDDs and SDs/week <15). Patients will be followed irrespective of whether they continue to receive treatment, so that analysis of both primary drinking measures and secondary outcomes will include all data available for the 12-week treatment period. Data for analyses of drinking outcomes during the 12-week treatment period will come from the daily IVR reports (missing IVR report days which will be coded as the larger of either 5 standard drinks (i.e. a HDD) or the IVR average daily use for the week reporting interval). Analysis of drinking for the 6-month follow-up period will be based on TLFB data collected at each follow-up visit. Secondary outcomes will include mean daily alcohol consumption, %dCDT levels (change relative to baseline), and severity of alcohol-related problems (as measured on the SIP and number of DSM-IV AD criteria).

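### The side-effect checklist is first given after dosing and the safety analysis has no new-or-worse rule, so checklist comparisons are diluted toward no difference by an amount the documents do not fix

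*Combined protocol and SAP*

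**What the plan says.** - **Timing.** C.6.b.3.c states: "Subjects will provide reports of side effects at each bi-weekly phone visit and study visit during the active treatment phase and 2-month follow-up visit". The row "Side Effect Checklist" in Table 1 is marked at the phone calls (weeks 1, 3 and 5), Visits 3 to 7, Visit 8 and Visit 9. Visits 1 and 2 are blank. C.3.a and C.4.b place the first dose at Visit 2, so the first checklist comes at the week 1 call.
- **Content.** The list covers "effects derived from prior studies of dutasteride". No onset date or comparison with pre-dose status is described.
- **Analysis.** C.8.a.1 builds AE summaries from this checklist, which "will be compared for patients receiving dutasteride or placebo using χ^2 analysis". The first comparison is "the number of patients in each of the two groups who report AEs"; the second is the same for moderate-to-severe AEs; the third is "the number of patients in each group who discontinue treatment due to AEs". Single AEs reaching 5% in either arm are also tested. No comparison requires the complaint to be new or worse.
- **Other pre-dose information.** There is a medical and psychiatric history at Visit 1 (C.4.a), and a physical examination with clinician history review, the BDI and the STAI at Visit 2 (Table 1). E.8 has AEs graded and assigned causality. None of this is linked to the C.8.a.1 comparison.

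**The concern.** Many checklist items, mainly sexual and general somatic complaints, can be present in heavy-drinking men before any study drug. A man who has such a complaint at Visit 2 and mentions it at week 1 is counted as reporting an AE. This happens in both arms, so it does not favour one arm, but it adds reports unrelated to treatment and shrinks the contrast.

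In an efficacy analysis dilution works against the hypothesis. Here it works for it: Aim 1 includes safety and expects the drug to be well tolerated, and the pilot summary in C.1.c already offers similar side-effect rates in the two arms as support for tolerability. Background complaints can also carry single items over the 5% testing threshold. Pre-dose status cannot be recovered reliably once dosing has begun.

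**Working it through.** **The plan's own power figure.** C.8.b states 80% power for d = 0.45 with 80 per arm at α = 0.05. Check: 0.45 × √(80/2) − 1.96 = 0.886, and Φ(0.886) = 81%. It reproduces, but concerns efficacy. No power is stated for safety.

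**Inputs for the safety check.** 176 randomised (C.8.b), taken as 88 per arm; two-sided α = 0.05. Let b be the share of men with the complaint before dosing (not in the documents, so varied), and q1 and q0 the new-onset rates on drug and placebo among men free of it. Assume equal b in both arms, every existing complaint reported, and no worsening.

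**Formulas.**
- Any-report rate, as planned: b + (1 − b)q in each arm.
- New-only rate, all 88 men as denominator: (1 − b)q.
- Power = Φ{[|A − B| − 1.96√(2p̄(1 − p̄)/88)] / √([A(1 − A) + B(1 − B)]/88)}, where A and B are the two rates and p̄ is their mean.

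The difference is (1 − b)(q1 − q0) under either count. The new-only count gains because its rates lie further from 50% and have smaller variance.

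**Worked case: assumed q1 = 15%, q0 = 3%, b = 20%.**
- As planned: A = 0.20 + 0.80 × 0.15 = 0.320; B = 0.20 + 0.80 × 0.03 = 0.224; p̄ = 0.272. Power = Φ[(0.096 − 1.96 × 0.0671)/0.0667] = Φ(−0.53) = 30%.
- New only: A = 0.120; B = 0.024; p̄ = 0.072. Power = Φ[(0.096 − 1.96 × 0.0390)/0.0383] = Φ(0.51) = 70%.

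| Background b | Any report, drug vs placebo | Power as planned | Power, new only |
|---|---|---|---|
| 0 | 15% vs 3% | 80% | 80% |
| 5% | 19% vs 8% | 60% | 78% |
| 10% | 24% vs 13% | 46% | 75% |
| 20% | 32% vs 22% | 30% | 70% |
| 40% | 49% vs 42% | 16% | 56% |

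**The protocol's own drug rates.** C.3.a.3 gives impotence 4.7% vs 1.7% at 0.5 mg daily in 2-year trials. Carrying these over to 12 weeks at the study dose is an assumption.
- No background: power 20% (18% by exact enumeration). Power of 80% would need about 540 per arm.
- b = 20%: 23.8% vs 21.4%, power 6% as planned (7% exact); new only, 3.8% vs 1.4%, power 17%.
- Three sexual items summed, assuming no overlap: 4.7 + 3.0 + 1.4 = 9.1% vs 1.7 + 1.4 + 0.5 = 3.6%. Power is 32% with no background. At b = 20% it is 10% as planned and about 26% new only.

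**The case against.** The strongest reply is that the size of the loss is assumed. That stands. Neither the pre-dose prevalence nor a 15% vs 3% effect is in the documents. A reader might infer that the comparison loses most of its ability to detect a drug effect. Under the illustration, 60 of 80 points of power remain at 5% background and 46 at 10%, so this is not established. At the documented impotence rates the trial has little power even with no background, and a baseline checklist would not cure that.

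A reader might also take the pilot in C.1.c as proof of heavy pre-existing complaints. It reports the "mean number of side effects reported / subject" as 6.0 (SD 5.8) on dutasteride and 8.4 (SD 10.8) on placebo, and sexual side effects in 3 and 4 men (7 of 39, or 18%). These reports were made after dosing and cannot be divided into old complaints, new events unrelated to the drug, and repeat reports. With SDs near or above the means, they do not show that nearly every man would be counted. New non-drug events would also remain after the fix.

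Nor do the documents support the inference that mood effects go undetected. BDI and STAI are taken at Visit 2 and repeated, and C.6.b presents the assessment of depression and anxiety as an added safety measure.

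Finally, the history, the clinician review and causality grading give partial information, and discontinuations due to AEs are not directly diluted. But none of these supplies an item-by-item baseline or enters the checklist comparison as written, so the gap remains.

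**Conclusion.** The concern holds in limited form. As written, complaints present before dosing count as AEs, which dilutes three checklist-based comparisons (any AE, moderate-to-severe AEs, single AEs) toward no difference. The arm comparison is not biased.

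The amount cannot be fixed from the documents. Under the assumed 15% vs 3%, with 5% to 40% background, the plan has 60% down to 16% power where a new-only count would have 78% down to 56%. At the quoted impotence rates with 20% background the figures are 6% and 17%, so sample size and dilution both limit what a null result can show. All figures rest on 1:1 allocation, equal background by arm, full reporting of existing complaints, and no worsening.

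This is a cheap improvement, not a flaw that invalidates the safety analysis.

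**What to change.** 1. Give the same checklist at Visit 2 before the first dose; add the mark in Table 1 and a phrase in C.6.b.3.c.
2. In C.8.a.1, count a checklist AE only if it is absent at Visit 2 or reported at a worse severity afterwards. Keep all randomised men in the denominator, and apply the 5% threshold for single items to this count.
3. Report the all-report counts as a supplement.
4. State that the sample size gives low power for effects as small as the quoted sexual side-effect rates, so that a non-significant test is not read as evidence of no effect.

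The cost is a few minutes per man at an existing visit, with an existing form. No new visit, staff or procedure is needed.
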